### Statistical Analysis

Primary Endpoint Analysis. *Accrual rate* will be defined as the number of YACS who agreed to participate divided by the number of weeks of recruitment. *Participation rate* will be defined as the percent of eligible participants who agreed to participate. *Retention rate* will be defined as the number of participants who completed 3-month measures divided by the number who consented to participate. Means and 95% confidence intervals will be computed for all rates. The proportion of patients who complete the 3-month assessment will be reported along with an exact 95% confidence interval. This percentage will also be reported for experimental condition individually. We will test the hypothesis that the recruitment rate is  $\leq 50\%$  vs.  $\geq 65\%$  using a one-sample test of proportions with a one-sided alpha level of 0.05. We will test the hypothesis that the retention rate is  $\leq 70\%$  vs.  $\geq 90\%$  using a one-sample test of proportions with a one-sided alpha level of 0.05. We will use a one-sample Poisson test to compare the average number of participants accrued per month with a null hypothesis of 12 participants per month and a one-sided alternative of 14 participants per month at an alpha level of 0.05.

Secondary Endpoint Analysis. Ratings of program acceptability and satisfaction will be summarized using descriptive statistics (mean, standard deviations, frequencies) of the post-treatment evaluation (Objective 2.1.3). Descriptive statistics (percentages, medians, interquartile ranges) will be used to estimate adherence to daily self-monitoring (Objective 2.1.4), and study measures relating to demographics, anthropometric, clinical, behavioral, and psychosocial measurements (Objectives 2.1.5-2.1.7.). These study measures will be reported at baseline and 3 months. We will also estimate changes in weight, anthropometric, clinical, behavioral, and psychosocial measures from baseline to 3 months, and within each experimental condition, the change scores

will be tested to see if they are significantly different from 0 using Wilcoxon Signed Rank tests.

Using maximum likelihood methods, we will use mixed model analyses with repeated measures to estimate changes in MVPA and HEI (and other secondary measures; Objectives 2.1.5-2.1.7) at 3 months and to test for statistical differences across conditions in changes over time, adjusting for age, cancer type, and time since diagnosis. Models will include random intercept, time, component, and component\*time variables. A proper error covariance structure will be chosen based on model fit indicated by model likelihood, Akaike Information Criterion and Bayesian information Criterion.

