## 4. STATISTICAL CONSIDERATIONS

### Sample Size and Power

The sample size is based on feasibility. Our primary feasibility measures are participation, accrual, and retention rates. Anticipated participation and retention rates are based on pilot feasibility studies among YACS and our previous work with this population. With an estimated participation rate of 85% (consistent with CO-I's experience, LCCC 1707), we anticipate it will be feasible to recruit 80 YACS within 6 months. We will test the null hypothesis that the proportion recruited is 50% or lower versus the alternative that it is 65% or greater using a one-tailed test at an alpha level of 0.05 with 95% power, which would support that the study is feasible.

We plan to accrue no more than 100 participants looking to have at least 80 evaluable participants, for 5 participants in each of the 16 groups. We expect accrual to take a total of 10 months at a rate of approximately 10 participants per month. We anticipate accruing 80 participants within 10 months, or 12-15 participants per month. A sample size of 80 achieves 99% power to detect a difference between a null hypothesis mean accrual rate of 12 participants/month and an alternative hypothesis mean of 15 participants/month with a significance level of 0.05 using a one-sided one-sample Poisson test.

For retention, we will test the null hypothesis that the retention is 70% or below versus the alternative that the retention is 90% or greater using a one-tailed test at a 0.05 alpha level. With 80 participants we would reject the null hypothesis that the retention is 70% if at least 62 participants are retained with 90% power, which would support that the study is feasible. With 80 participants we would reject the null hypothesis that the retention is 70% if at least 66 participants are retained with 97% power, which would support that the study is feasible.

All three endpoints must meet the proscribed criteria in order for the study to have successfully demonstrated feasibility.

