- C) Advertisements. We will place sponsored posts on social media, ads on relevant internet sites, and use email listservs. We will produce flyers, posters, brochures, and presentations to advertise the study at community events and cancer conferences dedicated to young adults (e.g., CancerCon, AYA Global Congress). We will work with the UNC AYA Oncology clinical staff with whom we have established relationships (i.e., Co-Investigator [name], Medical Director, UNC AYA Oncology; [name]) to advertise the study and recruit potentially interested individuals.

All recruitment efforts will direct participants to a study website with a more detailed description of the research study and FAQs about participating in research. Interested individuals will click through to a REDCap web screening survey to determine initial eligibility. Those who are preliminarily eligible will be contacted by trained study staff and will undergo additional phone screening. Following an approach we have used in the past, eligible and interested individuals will receive an email directing them to a unique REDCap link to an online informed consent. After providing consent, participants will be instructed on procedures for 1) completing one weekday and one weekend self-reported 24-hour dietary recall, 2) completing baseline online questionnaires, and 3) completing their baseline weight measurement. The Fitbit activity tracker will be mailed to the participant. After completion of baseline assessments, the participant will be randomized to one level of each of the 4 factors, or one of the 16 conditions (Table 1). The participant will be scheduled for a one-on-one telephone/videochat session during which they will be informed of condition assignments, assisted with downloading of the study smartphone app, and questions about getting started will be answered.

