## APPENDIX

Table 1. Experimental conditions in the 2 factorial trial

Core Intervention Components (ALL)	Experimental Condition	Nutrition Tracking (Green/Red Foods)	Nutrition Goals (Yes/No)	Text Messages (Yes/No)	Lessons (Once/Weekly)
Activity Tracker Traffic Light Log Weekly MVPA Goals Weekly Feedback	1	Green	Yes	Yes	Once
	2	Green	Yes	Yes	Weekly
	3	Green	Yes	No	Once
	4	Green	Yes	No	Weekly
	5	Green	No	Yes	Once
	6	Green	No	Yes	Weekly
	7	Green	No	No	Once
	8	Green	No	No	Weekly
	9	Red	Yes	Yes	Once
	10	Red	Yes	Yes	Weekly
	11	Red	Yes	No	Once
	12	Red	Yes	No	Weekly
	13	Red	No	Yes	Once
	14	Red	No	Yes	Weekly
	15	Red	No	No	Once
	16	Red	No	No	Weekly

[name]  
Principal Investigator

**PHYSICIAN CONSENT TO PARTICIPATE IN A DIET AND EXERCISE  
PROGRAM AT UNC-CHAPEL HILL**

TO: Physician's Name	RETURN TO:
	[name], RD
	UNC Weight Research Program
	Lineberger Comprehensive Cancer Center
	[name]
	[name]
	[contact]
City	[contact]
State	Email: [contact]
Zip	
(        )	Telephone Number

Your patient \_\_\_\_\_ has asked to participate in a lifestyle program at the University of North Carolina at Chapel Hill specifically designed for young adult cancer survivors to help them adopt healthier eating and activity habits.

The 3-month program is delivered using a study smartphone app and digital health tools. All participants will receive a standard program using the study smartphone app, which will have weekly lessons and feedback on progress. Each participant will receive a combination of tools to help them keep track of their diet and meet healthy eating and physical activity goals. The combination of tools will vary the method of dietary monitoring, physical activity goals, and personalization of study messages in the app for each study participant.

All participants groups will receive the following intervention:

1. A lifestyle program that focuses on physical activity and nutrition behavioral change, skills training, goal setting, and weekly feedback.
2. The physical activity program that will be primarily home-based. The exercise will gradually be progressed to 150 minutes per week with activities akin to brisk walking.
3. Behavioral modification techniques for changing eating and exercise behaviors.
4. Digital tools including a smartphone app and Fitbit activity tracker.

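### Wilcoxon signed-rank tests within each of 16 conditions of 5 participants cannot reach two-sided p < 0.05: the smallest exact p is 0.0625

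*Combined protocol and SAP*

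**What the plan says.** Section 4, Statistical Analysis (Secondary Endpoint Analysis), says of the 3-month changes in body weight and the other secondary measures that they "will be tested to see if they are significantly different from 0 using Wilcoxon Signed Rank tests". The tests are to be run separately by condition; the plan's words are "and within each experimental condition, the change scores". No alpha, sidedness, or choice between exact and asymptotic p-values is given for these tests. The two tests of proportions in the primary analysis, by contrast, are specified: "using a one-sample test of proportions with a one-sided alpha level of 0.05".

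The number of conditions is set elsewhere. The Recruitment section assigns every participant a level on all four factors and equates this with a single cell: "or one of the 16 conditions (Table 1". The appendix table that lists the cells, whose title begins "Table 1. Experimental conditions in the", has a column called Experimental Condition, numbered 1 to 16.

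The cell size is in Sample Size and Power. The accrual limits come first: "We plan to accrue no more than 100 participants looking to have at least 80 evaluable participants". The same sentence then turns the lower figure into a planned cell size, "for 5 participants in each of the 16 groups".

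The comparison of components is a separate analysis, a repeated-measures mixed model. Its list of terms opens "Models will include random intercept, time, component, and", and the interaction of each component with time carries the comparison.

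**The concern.** A signed-rank test on a handful of participants has few attainable p-values. If the smallest of them exceeds the significance level, the test cannot reject whatever the data show, and the planned cell size of 5 is in that range for a two-sided 0.05 test. The plan would then produce 16 non-significant results for every outcome, which a reader could take as evidence that nobody changed. Alternatively, with a normal approximation, it could produce nominally significant results whose error rate exceeds the stated level. Because the method is unspecified, the choice between these could be left to a software default.

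**Working it through.** **Inputs.** 80 evaluable participants, 16 conditions, accrual cap of 100 and retention hypotheses of 70% and 90% (all from Section 4). The alpha for the signed-rank tests is not stated; I assume 0.05, the level the plan uses for its primary tests. Sidedness is not stated either; a test of whether change differs from 0 reads as two-sided.

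**Cell size.** 80/16 = 5, which reproduces the plan's own figure. The synopsis gives 72 subjects, which would be 72/16 = 4.5 per cell.

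**Smallest attainable exact p.** Under the null each of the 2^n sign patterns is equally likely, and the most extreme result is all signs alike. The minimum two-sided p is therefore 2/2^n.

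| Non-zero changes in the cell | Minimum exact two-sided p |
|---|---|
| 4 | 2/16 = 0.125 |
| 5 | 2/32 = 0.0625 |
| 6 | 2/64 = 0.031 |
| 7 | 2/128 = 0.016 |

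The first cell size at which the test can reject is 6, and then only if all six changes agree in sign. An exact one-sided test at n = 5 could reach 1/32 = 0.031.

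**Dependence on the method.** For five untied changes in the same direction the rank sum is 15, its null mean is 7.5 and its variance is 5·6·11/24 = 13.75 (SD 3.708).

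- Exact: p = 0.0625.
- Normal approximation with continuity correction: z = 7.0/3.708 = 1.888, p = 0.059.
- Normal approximation without correction: z = 7.5/3.708 = 2.023, p = 0.043.

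The uncorrected version rejects only when all five signs agree, which happens with probability 2/32 under the null. Its true size is therefore 6.25%, not 5%. Over 16 separate cells of 5, the chance of at least one false positive for a given outcome is 1 − (1 − 0.0625)^16 = 0.64.

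**How many cells could reach 6.** Having 6 in all 16 cells needs 6 × 16 = 96 completers. At 10% dropout that is 96/0.9 = 107 enrolled, above the cap of 100. Assume cells balanced at enrolment and independent dropout:

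- 80 enrolled: 16 cells of 5, so none can reach 6.
- 100 enrolled (4 cells of 7, 12 of 6), 80% retained, which gives the plan's 80 evaluable: 4(0.577) + 12(0.262) = 5.5 cells expected.
- 100 enrolled, 90% retained: 4(0.850) + 12(0.531) = 9.8 cells expected.

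**Power where rejection is possible.** The documents give no SD, so I take normal changes with mean d SDs. At n = 6, power = Φ(d)^6 + Φ(−d)^6: 0.11 at d = 0.5, 0.24 at d = 0.8, 0.35 at d = 1.0, 0.66 at d = 1.5 and 0.87 at d = 2.0. For d = 0.5, simulation with exact critical values (40,000 runs) gives 0.86 at n = 40, the size of one factor level, and 0.99 at n = 80, the whole sample.

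**The case against.** The strongest objection is that the word condition may not mean a Table 1 cell. The Nutrition Goals text uses it for a single factor level (the red or green food condition). The mixed-model paragraph speaks of differences across conditions although its only intervention terms are components. At factor-level size, about 40, the problem disappears. This reading is possible, but Table 1 uses the same phrase as its column heading for the 16 cells, so the cell reading is likelier. Under either reading the term needs defining.

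Second, the impossibility is conditional. A one-sided exact test or an uncorrected approximation can reject at n = 5. With heavily tied changes, likely for the FRAIL index (an integer from 0 to 5), a continuity-corrected approximation can too: p = 0.048 with four of five tied and 0.037 with all five tied. That is correct. But ties do not alter the count of 32 sign patterns, so the exact two-sided minimum stays at 0.0625, and the approximations reject only by understating it.

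Third, exact balance is an assumption, since no blocking is described. Under simple randomization the expected number of cells with 6 or more completers is 6.1 (80 enrolled, full retention), 4.7 (80, 90%), 7.9 (100, 90%) or 6.1 (100, 80%). The zero at 80 enrolled therefore depends on balance. Some cells would be larger, but others would be smaller than 5. Multiple imputation, which the plan mentions, might bring analyzed cells to 6 or 7 if 100 are enrolled. However, its trigger refers to predictor variables, and pooling of signed-rank tests is not described. Very large changes could also be detected at n = 6, as the power figures show.

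Finally, this is a feasibility pilot that lists its sample size as a main limitation, and no feasibility decision rests on these tests. That limits the severity. The stated limitation is about inconclusive effect sizes, though; it does not tell the reader that a planned test cannot reject at the planned cell size.

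**Conclusion.** The concern holds. At the planned 5 per condition, an exact two-sided 0.05 signed-rank test has zero power for any effect, because its smallest p is 0.0625. This needs no assumption about SDs. It does rest on condition meaning the 16 Table 1 cells, on a two-sided 0.05 level, and on an exact p-value. If accrual exceeds 80, some cells may reach 6 or more, but not all 16 can under the cap at 10% dropout with completers only, and power there is low for moderate changes. This is a moderate error in a secondary analysis that should be fixed before analysis. The three primary feasibility tests and the component-by-time contrasts are not affected.

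**What to change.** - Remove the significance tests within the 16 cells. Report change in each cell descriptively: n, median, interquartile range and individual values.
- Estimate change from baseline with 95% confidence intervals in the whole sample (about 80) and at each level of each factor (about 40, averaged over the other three factors). Take these from the mixed model already planned, or use a two-sided signed-rank test at that level for skewed measures.
- For any signed-rank test that is kept, state alpha, sidedness and exact or asymptotic method, including the handling of ties and zero changes.
- Define experimental condition as the 16 cells of Table 1, and use factor level for the two arms of a single component.

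The cost is SAP wording and table shells; no new data or participants are needed. What is lost is cell-specific p-values, which the planned cell size cannot usefully supply. The factor-level estimates share participants across factors and are uncontrolled pre-post changes, so they describe change and do not replace the component-by-time contrasts.

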**Exclusion Criteria**

1. History of heart attack or stroke within past 6 months
2. Untreated hypertension, hyperlipidemia, or diabetes, unless permission is provided by their health care provider.
3. Health problems which preclude ability to walk for PA
4. Report a heart condition, chest pain during periods of activity or rest, or loss of consciousness on the Physical Activity Readiness Questionnaire (PAR-Q; items 1-4).
5. Report a past diagnosis of or receiving treatment for a DSM-IV-TR eating disorder (anorexia nervosa or bulimia nervosa).
6. Currently pregnant, pregnant within the past 6 months, or planning to become pregnant within the next 6 months.
7. Hospitalization for depression or other psychiatric disorder within the past 12 months. History of psychotic disorder or bipolar disorder.
8. Plans for major surgery (e.g., breast reconstruction) during the study time

---

frame

9. Currently participating in a weight loss, nutrition or physical activity study or program or other study that would interfere with this study.
10. Currently using prescription weight loss medications

Number Of Subjects	72
Study Duration	Each subject's participation will last 4 months.
Study Phases	
Screening	(1) Screening : screening for eligibility and obtaining consent and (2) Baseline assessment
Study Treatment	(3) Intervention : study intervention/experimental treatment.
Follow-Up	(4) Follow-up assessment will occur at 6 weeks and 3 months
Efficacy Evaluations	NA
Pharmacokinetic Evaluations	NA
Safety Evaluations	All medical events and safety data will be assessed at assessment points or when interim events are reported by participants using a standard form used in our ongoing NIH funded trials.
Statistical And Analytic Plan	
The primary objective is to evaluate the feasibility and acceptability of a digital intervention components to increase PA and improve nutrition behaviors among YACS (n=80) at 3 months. Our primary feasibility measures are participation, accrual, and retention rates.
 
The secondary outcome analysis will use mixed effects models to test for differences in MVPA and HEI by intervention components across time (baseline, 6 weeks, and 3 months). Effects will be modeled as component x time interactions with the 3-month outcome as the primary endpoint.

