## 1. STUDY OBJECTIVES

Few studies have tested PA interventions specifically for YACS, and no studies have tested nutrition interventions among this population. To accelerate science in this area, we propose a pilot randomized factorial trial to test the feasibility, acceptability, and effects of a digital PA and nutrition intervention designed specifically for young adult cancer survivors. Previous interventions have demonstrated the importance of self-regulation (i.e., self-monitoring of behaviors, small changes, goal setting and feedback) approaches to improve PA and nutrition behaviors among young adults and YACS. We aim to leverage our prior work to deliver a theory-based intervention using digital tools to simplify self-monitoring of PA, dietary monitoring, and self-weighing to provide tailored behavioral goals and messages to support increased physical activity and diet quality among YACS.

Using a factorial experiment, we will test main effects of each of 4 candidate intervention components and interactions between the components, making efficient use of a smaller sample size than a typical RCT would require. We propose to conduct a 3-month, 2 full factorial trial testing the effects of four intervention components—each with two levels—including (Table 1):

- 1) simplified dietary tracking based on TLA (daily tracking of green (low-calorie, high nutrients) vs. red (high-calorie, high-fat, low nutrients) foods),
- 2) dietary goals using TLA (daily goals vs. no goals),
- 3) supportive text messages (yes vs. no),
- 4) lesson delivery (all provided once vs. weekly).

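### The mixed models are specified by maximum likelihood with no small-sample degrees of freedom, so component-by-time standard errors are about 3–4% too small as written, and more so if component interactions are added

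*Combined protocol and SAP*

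**What the plan says.** The secondary analysis in Section 4, Statistical Analysis, reads "Using maximum likelihood methods, we will use mixed model analyses with repeated measures". Its purpose is to estimate change at 3 months and "to test for statistical differences across conditions in changes over time", "adjusting for age, cancer type, and time since diagnosis". The terms are given as "Models will include random intercept, time, component, and" the component-by-time product. On covariance, "A proper error covariance structure will be chosen based on model fit", judged by likelihood, AIC and BIC. No REML, no degrees-of-freedom method, no reference distribution and no alpha are given for these tests.

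The Synopsis (Statistical and Analytic Plan) also describes component-by-time effects, with 3 months as the endpoint, and its objectives mention main effects only. Section 1 goes further: "we will test main effects of each of 4 candidate intervention components and interactions between the components". The Nutrition Goals paragraph in Section 2 likewise intends to look at the interaction of dietary monitoring with goals.

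Sample Size and Power plans "at least 80 evaluable participants, for 5 participants in each of the 16 groups". The Synopsis row "Number Of Subjects" gives 72, although its analysis paragraph gives 80.

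Section 3 (Data Collection; Behavioral Measures) collects MVPA and HEI at baseline and 3 months only. The Synopsis models them at baseline, 6 weeks and 3 months.

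**The concern.** Maximum likelihood variance estimates make no allowance for the fixed effects that were fitted. In a large trial this is negligible. With 72–80 people it is small but visible for four components, and it grows as interaction terms are added. A normal or chi-square reference adds a second, separate optimism. Together they make confidence intervals too narrow and p-values too small for the component effects that this pilot will pass on as preliminary evidence.

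The covariance rule does not help. With two time points, a random intercept already implies equal variances and one covariance. An unstructured 2×2 matrix has three free quantities, so adding a random intercept to it gives four parameters for three quantities, which cannot be identified. Choosing among such structures by AIC or BIC provides no small-sample correction.

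**Working it through.** **Inputs.** n = 80 (Sample Size and Power) or 72 (Synopsis). As a low case, n = 62 completers, the smaller retention count that Sample Size and Power treats as supporting feasibility. Sixteen conditions (Appendix, Table 1). Assumptions, because the plan is silent: two-sided 5% tests, literal maximum likelihood, two time points and complete pairs.

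**The plan's own figure.** 16 × 5 = 80 reproduces the evaluable total; 72/16 = 4.5 per condition. The plan states no error rate or power for the mixed models, so there is nothing further to reproduce.

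**Step 1: reduce the model.** With two time points and complete pairs, the component-by-time test from a random-intercept model equals a regression of change on the components. Covariates entered without a time interaction cancel from the change. The number of fitted effects p is:
- 5 for the model as written (time plus four component-by-time terms);
- 11 with all six two-way interactions by time (5 + 6);
- 16 for the saturated model (11 + 4 three-way + 1 four-way).

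**Step 2: standard errors.** ML uses SSE/n where REML uses SSE/(n − p), so SE(ML)/SE(REML) = √((n − p)/n). For example, √(75/80) = 0.968 and √(67/72) = 0.965.

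**Step 3: single-test error.** The true reference is t on n − p degrees of freedom. Against a normal critical value, error = P(|t| > 1.96 × ratio). At n = 80, p = 5 this is P(|t₇₅| > 1.898) = 0.062. Against a t critical value, 1.96 is replaced by the 97.5% point of t on n − p degrees of freedom.

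| Model | n | SE ratio | Error, z | Error, t |
|---|---|---|---|---|
| As written, p = 5 | 80 | 0.968 | 6.2% | 5.8% |
| | 72 | 0.965 | 6.3% | 5.8% |
| | 62 | 0.959 | 6.5% | 6.0% |
| All two-way, p = 11 | 80 | 0.929 | 7.3% | 6.8% |
| | 72 | 0.920 | 7.6% | 7.1% |
| Saturated, p = 16 | 80 | 0.894 | 8.4% | 7.9% |
| | 72 | 0.882 | 8.9% | 8.3% |

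**Step 4: a joint 15-df test, if one were run.** With q = 15, the ML Wald statistic is qF·n/(n − p) and the likelihood-ratio statistic is n·log(1 + qF/(n − p)). Both are compared with the chi-square 95% point, 25.0.
- ML Wald: 21% (n = 80) and 24% (n = 72).
- Likelihood ratio: 11% and 12%.
- REML variance with the same chi-square reference: 8.1% and 8.5%. Part of the inflation therefore comes from the reference distribution and not from ML.

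**Step 5: simulation check.** Random-intercept ML and REML fits, about 1,500 runs per setting, used an assumed intraclass correlation of 0.5, the three covariates (four cancer-type levels assumed) and 0% or 20% dropout. For the model as written, single-test error under ML with a normal reference was 5.8–6.5%. For the 16-condition model it was 8.3–10.7%. REML with an F reference gave 4.0–5.5% for the joint tests.

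**The case against.** The best defence is that the written model contains component and component-by-time terms only, and the Synopsis agrees. A reader might infer that the planned tests carry 12–24% error. The documents do not support that. They specify no 16-level condition factor and no 15-df joint test. The reading rests on the phrase about differences across conditions and on the interactions promised in Section 1, which the model statement does not carry through. This part of the defence stands, so the larger figures are conditional.

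Second, the plan names no reference distribution. Software that uses t on n − p degrees of freedom would bring the error for the model as written to about 5.8%. That stands too: the effect is reduced, not removed.

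Third, the reference to maximum likelihood methods may be a loose label that includes restricted maximum likelihood. If so, the standard-error part falls away. The missing degrees-of-freedom method would remain.

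Fourth, a reader might infer that biased tests will decide which components go forward. Strengths and Limitations already says that the effect sizes may not be conclusive for such decisions, and Section 1 calls the evidence preliminary. That caveat limits the harm, but it does not correct an understated standard error.

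Finally, for outcomes measured three times, choosing a covariance structure by AIC or BIC is ordinary practice. The criticism of that rule holds only where Section 3's two time points govern.

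**Conclusion.** The point holds at modest size. For the model as written, standard errors are about 3–4% too small and a nominal 5% test runs at about 6% (5.8–6.3% at 72–80 participants, depending on the reference; 6.0–6.5% with 62 completers). If interactions are added, the error is about 7–8% per test with all two-way terms and about 8–9% in the saturated model. The joint-test figures of 11–24% describe an analysis that the plan does not commit to, and they are partly due to the chi-square reference.

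The conclusion assumes literal ML, a two-sided 5% level, complete pairs and two time points; the simulation with dropout supports the same pattern. These are secondary endpoints of a pilot sized for feasibility. The participation, accrual and retention conclusions do not depend on them. This is a worthwhile refinement, not a flaw that threatens the trial.

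**What to change.** In Section 4, Statistical Analysis:
- State that all mixed-model tests and confidence intervals use REML with Kenward-Roger (or Satterthwaite) degrees of freedom. Both parts are needed, because REML with a chi-square reference remains too liberal for joint tests. Keep ML only for comparing models with different fixed effects.
- State whether tests are by component or by condition, and list any component-by-component-by-time terms that will be fitted.
- Reconcile the two time points for MVPA and HEI in Section 3 with the three in the Synopsis. For outcomes measured only at baseline and 3 months, use one unstructured 2×2 covariance without an added random intercept, in place of AIC/BIC selection.

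The cost is a few sentences and a software option. Confidence intervals widen slightly: by about 3–4% from the estimator alone in the model as written (1/0.968 = 1.033; 1/0.965 = 1.036), and a little more from the t reference.
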